**Using IT to improve access, communication, and asthma in African American and Hispanic/Latino Adults
NCT 02086565**

June 25, 2018

METHODS AND DATA ANALYSIS

Study Overview

The overall study design has been previously published.¹ We describe methods in full here, and in more detail in the attached appendix (Appendix A). Adults with uncontrolled asthma, generally unfamiliar with the patient portal, were recruited from outpatient primary care and specialty clinics of two health systems that serve predominantly but not exclusively low-income urban neighborhoods. Participants were trained in the use of the portal: Portal Training (PT). Participants were then randomized 1:1 to home visits (HV), from a Community Health Worker (CHW, described below), to encourage use of the portal and to facilitate care coordination or no home visits. The project was approved by the University of Pennsylvania Institutional Review Board and was registered with ClinicalTrials.gov (NCT02086565).

Study design

We chose a randomized controlled trial (**HV + PT versus PT**) because randomization reduces the likelihood of bias from both known and unknown confounders.² The longitudinal design supports baseline measures as within-subject controls and the multicenter recruitment also enhances the generalizability to a diversity of social circumstances.

The choices for the randomized trial, portal training (PT) and home visits (HV), were inspired by the RE-AIM conceptualization framework³ and the need for implementation research.⁴ Implementation of portal training and home visits were hypothesized to improve access and communication resulting in improved patient-centered outcomes including asthma control and asthma-related quality of life.

Those randomized to PT+HV worked with the same CHW who conducted both portal training sessions. At each home visit, the CHW ensured care coordination, including obtaining an asthma action plan that linked patients' home and community with the clinic. The CHW provided standard asthma education, promoted communication with providers, encouraged appointment keeping, and facilitated familiarity with health information technology.

Study setting

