*Three literacy measures were used: Asthma Numeracy Questionnaire,³⁹ the Short Test of Functional Health Literacy in Adults,⁴⁰ and Electronic Health Literacy.⁴¹ Electronic health literacy was measured with the eHEALS, the eHealth Literacy Scale, an 8-item measure of knowledge, comfort, and perceived skills at finding and evaluating electronic health information.⁴¹ It has been used in low-income patients.⁴² Each item is measured with a 5-point likert scale and the eHEALS score is the mean of each item.

**The Medical Outcomes Study Social Support Survey.^{43,44}

Our working hypothesis was that patients with comorbidities and with limited computer literacy might (a) not benefit from portal education at all, and (b) might have additional benefit with the home visitor intervention. Further details appear in Appendix A6.

Statistical Analysis plan

Testing within-group effects over the time of the study allowed us to assess the effect of each intervention. In brief, the within-group change in the PT group allowed measurement of PT alone. Subtracting any change over time in the PT+HV group from the PT group allowed estimates of the additional effect of home visits.

Intention to treat approach –primary analysis

The primary analysis was “as randomized” (intent to treat), with the assumption that any dropout visits were missing completely at random (MCAR). The estimand of interest was the difference between the home-visitor versus portal-only groups in the change in outcomes over time. We attempted to use mixed effects models, which make less strong missing at random (MAR) assumptions, with varying success. (Details appear below and in the analysis-specific appendix, Appendix A).

Modeling approach – flexible modeling of time

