Appendix A7 (continued). Methods for handling Irregular data collection interviews - Unified modeling approach.

differ from the same patient's measurement at month 12. Fourth, although multiple imputation is a well-accepted option for missing outcomes when visit times are categorical, the approach is not practical when, as in our case, visit times can and do occur throughout the 12-month follow-up. Multiple imputation, as currently programmed, would necessitate that we impute all 12 months of data for each patient – a very large amount of missing observations to impute and thus a large fraction of monthly outcomes are missing by design. Finally, examples in the statistical literature support this suggested approach (Howe 2016).

Model form

The primary outcome is improvement in asthma control in both the intervention (PT + HV) and the control PT (Portal only) groups. The question of interest then is whether asthma control improved over time more in the PT + HV group compared to the control group, and did the control group improve over time. More formally, as the primary comparison of this primary outcome, the corresponding statistical estimand is the difference in expected values between the PT + HV group and the PT (control) group from baseline to 12 months after randomization date. To test the within group and across group effects of the interventions on outcomes we implemented mixed effects models (using restricted maximum likelihood and adaptive quadrature) and marginal models (using generalized estimating equations (GEE)) as a unified approach for the analysis of the longitudinal data with baseline randomization. For within-group outcomes, these models use all available data to estimate changes over time. Both the mixed effects and marginal models can be used for continuous, binary, and count outcomes using linear, logistic, and log linear models that can compare changes over time in the outcomes of asthma control, quality of life, ED visits, hospitalizations over one year. (Fitzmaurice, Laird, Ware 2011). By including group-by-time interaction terms, these models can then be adapted to compare improvement over time between the patient portal plus home visit group and the portal only group.

Each type of model has its strengths and weaknesses. While the GEE method benefits from simplicity and robustness, it requires stronger assumptions about dropout (dropout

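### The SAP reads pre-post change in the portal-training arm as the effect of portal training, but every participant is trained, so the design does not identify that effect

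*Combined protocol and SAP*

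**What the plan says.** The opening paragraph of the Statistical Analysis plan section makes two attributions: "Testing within-group effects over the time of the study allowed us to assess the effect of each intervention", and then "In brief, the within-group change in the PT group allowed measurement of PT alone". A third sentence takes the difference between the two arms' changes as the added effect of home visits.

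Appendix A7 (Model form) repeats the within-group language: "To test the within group and across group effects of the interventions on outcomes we implemented mixed effects models". It also asks, next to the comparison of arms, "and did the control group improve over time".

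The Study design section treats both components as active: "Implementation of portal training and home visits were hypothesized to improve access and communication resulting in improved patient-centered outcomes". The Study Overview, the Recruitment section and Table 1 show that all participants consent to PT and are trained. The 1:1 randomisation concerns home visits only.

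**The concern.** A change from baseline in one arm is not a treatment effect unless something in the design shows what would have happened without the treatment. For home visits, the PT arm does that. For PT, nothing does. Yet the SAP states as fact that PT-arm change measures PT alone.

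What is at stake is the conclusion about one of the two components that the trial hypothesises to be beneficial. If the PT arm improves and its interval excludes zero, the SAP as worded licenses the statement that portal training improved asthma control. The test of change could be correct and the attribution still unfounded. The planned sensitivity analyses do not help, because their endpoint is fixed as the between-group difference in change.

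**Working it through.** **1. Is there any comparator for PT?**

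| Element | Where | What it provides |
|---|---|---|
| Consent | Recruitment | All consent to PT; a second consent covers home visits only |
| Randomisation | Study Overview, Study design | PT+HV versus PT, 1:1 |
| PP1 and PP2 training sessions | Table 1 | Delivered in both arms |
| Untrained arm, run-in, external control, stated no-change assumption | Nowhere in the documents | Nothing |

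The one design feature offered for within-person reading is this: "The longitudinal design supports baseline measures as within-subject controls". Using each patient's own baseline removes stable differences between patients. It does not remove change over time that has other causes.

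**2. What else could move the PT arm?** The documents themselves point to several sources:
- Entry required prednisone, an emergency visit or a hospitalisation for asthma in the past year (Inclusion criteria), so some regression to the mean or recovery is possible.
- Patients stay under usual care at the participating clinics.
- The PT column of Table 1 lists email or phone prompts, and data are collected quarterly.
- Appendix A10, on the exclusion restriction, allows that patients in both arms might expect some improvement simply from being recruited and followed.

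No section connects these back to the attribution or withdraws it.

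**3. Does the plan's own power figure bear on PT?** Statistical power gives 0.82 to 0.87 for a between-group difference of 1/3 SD with 300 evaluable, balanced. With 150 per arm and an assumed two-sided alpha of 0.05:

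SE = sqrt(2/150) = 0.1155 SD; 0.3333/0.1155 = 2.887; power = Phi(2.887 - 1.96) = 0.823.

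This matches the lower end. Adjusting for baseline multiplies the SD by sqrt(1 - rho^2). At an assumed rho of 0.35 that factor is 0.937, and power = Phi(3.082 - 1.96) = 0.869, close to the upper end. The stated power is therefore power for the randomised contrast and says nothing about a PT effect.

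**4. Illustration of misattribution.** The documents give no ACQ SD, no within-person correlation and no background change, so all three are assumed. Work in SD units, with equal SD at both times, a true PT effect of zero, 150 patients in the PT arm, background improvement d, and a two-point test at the two-sided 5% level, counting only the improvement direction:

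SE = sqrt(2(1 - rho)/150); P(significant improvement) = Phi(d/SE - 1.96).

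| rho | SE | d = 0 | d = 0.1 | d = 0.2 |
|---|---|---|---|---|
| 0.3 | 0.0966 | 0.025 | Phi(-0.925) = 0.18 | Phi(0.110) = 0.54 |
| 0.5 | 0.0816 | 0.025 | Phi(-0.735) = 0.23 | Phi(0.489) = 0.69 |
| 0.7 | 0.0632 | 0.025 | Phi(-0.379) = 0.35 | Phi(1.202) = 0.89 |

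Drift common to both arms cancels in the difference of changes, so the between-arm contrast keeps its nominal error rate.

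**5. A side matter.** The Study Overview has training before randomisation; Table 1 has randomisation and baseline at week 0, before PP1 and PP2. Month 0 is the randomisation date. If the Overview order held, the measured change would start after training. The two places should be reconciled, but PT is not identified under either order.

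**The case against.** The strongest reply is that the formal statements are all between-group: the estimand and contrast in the SAP, the sensitivity endpoint, and the estimand in Appendix A7, which also calls the PT arm the control. On that view the fault is a little introductory prose, and the documents report no conclusion that PT worked. This stands as a limit on scope. It does not cure the two sentences, which assert something the design cannot deliver and are nowhere qualified.

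Several stronger readings are tempting, and the documents do not support them:
- *Appendix A7 makes within-group improvement the primary analysis.* It does say "The primary outcome is improvement in asthma control in both the intervention (PT + HV) and the control PT (Portal only) groups", but the same paragraph then defines the formal estimand as the difference between arms. Asking whether the control arm improved is legitimate description.
- *Describing baseline as a within-subject control is itself an error.* It is ordinary change-from-baseline language and does not claim to replace an untrained arm.
- *The fraction achieving control is offered as proof of a PT effect.* The section on alternative approaches makes no PT claim. The section on heterogeneity of treatment effect and Appendix A6 gloss the intervention as home visitors.
- *A spurious change would be recognisable because its estimate would fall below the 0.5-point important difference.* This confuses true drift with its estimate. Since 1/3 SD is said to be below 0.5, the SD is below 1.5. With 0.3 SD of drift and SE 0.0816 SD, the chance of an estimate above 0.5 is 1 - Phi((0.5 - 0.30)/0.0816), about 1%, at SD 1.0, and 1 - Phi((0.5 - 0.45)/0.1225), about 34%, near SD 1.5.

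It is also fair to say that the size of any drift is unknown. The qualifying event could fall anywhere in the past year, the ACQ covers the past week, no ACQ threshold is listed for entry, and Appendix A10 speaks only of possible expectations.

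**Conclusion.** The concern holds as a matter of identification: the SAP claims that PT-arm change measures PT, and a design in which everyone is trained cannot show that. The same limit applies to pre-post change in the PT+HV arm, which on its own is not the effect of the combined package. This conclusion needs no numerical assumption.

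The percentages above are illustrations under assumed drift, correlation and equal SDs. They are not estimates of bias in this trial. They show that modest background improvement can often produce a significant PT-arm change when PT does nothing.

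A reader might infer that the trial's main comparison is compromised. It is not: the randomised PT+HV versus PT estimand, contrast, sensitivity endpoint and power stand. Nor do the documents show that a PT effect has been claimed in results. The fault is in what the SAP says may be concluded about PT.

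**What to change.** - **Statistical Analysis plan, opening paragraph.** Replace the two attribution sentences with: *Within-group changes are uncontrolled and reported descriptively. Because all participants received PT, the design does not identify a PT effect.* Keep the sentence on the additional effect of home visits.
- **Appendix A7, Model form.** Refer to within-group changes and across-group effects, instead of within-group effects of the interventions. Mark the control-group question as descriptive and not attributable to PT.

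No edit is needed to the Study design wording on baseline measures or to the section on alternative approaches for asthma control.

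The cost is wording, plus giving up a PT efficacy claim that the design cannot support. Sample size, power and the primary estimator do not change.

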Using guidance and policies of the supervising institutional review board and the participating health care systems, we recruited patients as follows. After explaining the protocol in staff meetings of participating sites, we received lists of potentially eligible patients (age ≥ 18 years, asthma in problem list of the electronic health record, prescribed an inhaled corticosteroid, having an address in one of the low-income neighborhoods) for whom further screening was needed. First we sent “opt-out” letters to clinicians asking for permission to contact their patients. If providers either did not respond to two letters or gave permission, we sent letters to potential participant patients asking to contact them for screening. If patients gave permission, or did not respond, we called the potential participant or approached them at a clinic visit to explain the study and ask for permission to screen for eligibility. According to their preference, we screened potential participants at their clinic or in their home. Data collectors completed a screening form for each patient contacted for recruitment which included a section to document reasons for declining. The following are reasons for declining: inability to commit to study timeline, disinterest in research participation, and patient illness. Participants all signed informed consent to enroll in the study and to undergo Portal Training and data collection. Those randomized to home visits signed a second consent form informing them they were also randomized to home visits and giving permission for these visits.

Randomization and allocation concealment

Randomization was stratified by clinical site. To maintain allocation concealment, we implemented randomly permuted blocks with varying block sizes (2 to 4). For each clinic we prepared opaque envelopes and instructions on how to preserve allocation concealment until the patient gave consent and the envelope was unsealed. Randomization programs and envelopes were prepared under the supervision of one of the project statisticians.

Interventions and Comparators: Portal Training and Home Visit with Community Health Worker

Community Health Worker (CHW)

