CHWs live in the community and are familiar with the environment; are acceptable to patients; and connect patients to health education, services, and the health care setting.⁵⁻⁷ In our Community Asthma Prevention Program (CAPP), we identified and trained CHWs as lay health educators to provide home asthma education and environmental intervention. Over 20 years, CAPP CHWs have visited 3000+ families with children⁸ in both African American (West Philadelphia) and Hispanic/Latino (North Philadelphia) communities, the same communities for the current project. These CHWs have a high school education or greater with at least three years' work experience and personal knowledge of asthma. They bring their knowledge as a community resident to suggest local resources to meet daily needs. CHWs are able to establish relationships with participants and their families to promote better asthma self-management, connection with community resources, communication with providers and mitigation of asthma triggers. CAPP's CHWs have functioned not only as home visitors, but also as asthma navigators who have been integrated into the health care team, providing a direct link between families and clinicians. Our experience has allowed us to develop an excellent support system including supervision, training, and systems for scheduling visits and data entry.⁹ The retention rate of participating families in CAPP has been above 90%.¹⁰ Home visits for children with asthma often include tailored asthma education and environmental remediation of allergen and irritant environmental exposures.

In the current intervention, each home visit included 1) reinforcement of the use of the portal and 2) care coordination (Table 1). Our activities were unique in utilizing CHWs for home visits for promotion of portal use with the intention of linking the patient to the medical practice, thereby improving patient-physician communication, a known contributor to asthma disparities. The home visits focused on communication and access, the same goals as potentially achievable through portal use.

Table 1. Activities and data collection (DC) for PT+HV and PT groups.

Time	PT+HV	PT
DC- Week 0	Participant meets with a member of the research team for consent, enrollment, randomization, and baseline data collection. This data collector is not the CHW who provides PP1, PP2 or HVs (if participant is randomized to HV).	

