Irregular data collection times (see results) required models that used outcome time as a continuous measure. For that reason, analysis models implemented spline based marginal (GEE) (MCAR assumption) and mixed effects (MAR assumption) longitudinal models, both identity/Gaussian, log/Poisson, and log/gamma with marginal splines to estimate expected values of outcomes at 0 months and 12 months and outcome changes between 0 and 12 months. We used all data collection times and the actual times. We did not artificially categorize data collection times to equate to the preplanned 0, 12, 24, 36, and 48 weeks from randomization. The contrast (estimator) of interest was the difference between the treatment groups in the changes in expected values from 0 months to 12 months. Examples in the statistical literature support this approach.⁴⁵ All confidence bounds were estimated using 999 bootstrap resamples (percentile-based). By using 999 samples, confidence bounds are from the 25th and 975th order statistics without interpolation. Details appear in Appendix A7.

Model form

We used both marginal and mixed effects models, with the marginal model being the primary approach owing to convergence problems with mixed effect models (noted below).⁴⁶ By including splines for time and group-by-time interaction terms, these models could produce the expected values at 0 and 12 months and predicted values of interest.

For the primary outcome of asthma control, the skewed distribution of outcomes necessitated that we use log gamma models. The treating clinic was a stratifying factor in all models to account for the stratified randomization.

Alternative approaches for estimating asthma control

Differences between intervention groups in expected values at given follow up times, although statistically appropriate for comparing groups, lacks an immediate connection to the manner in which clinicians might want to interpret results. For that reason, we pre-planned two methods for translating findings into clinically useful metrics.

(1) Fraction of patients who have achieved asthma control (a level below 1.5 on the scale):

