We avoided dichotomizing data, an ad hoc approach, but instead used mixed effects linear model and predictions to report the change in the fraction of patients who achieved adequate control. This prediction accounts for patient variation about the expected value and in theory represents a better estimate of the patient's true outcome (asthma control) than does the patient's observed value. Once we estimated each patient's predictions at baseline and at 12 months, we dichotomized these model-based predicted values to estimate the fraction of patients who achieved asthma control at baseline and at 12 months in each group. This is not the primary analysis, however, but represents an alternative demonstration of intervention effectiveness. Details appear in Appendix A8.

(2) Minimally important improvement: For estimates of the improvements at the patient level on the asthma control (Juniper) scale, the minimally important difference is 0.5.^{23,47} Again, the model-based predicted values are the best estimates at the individual level of the level of asthma control at a given time and account for measurement error as well as variation across individual patients. We compared changes in individual predictions of asthma control at 0

months and 12 months and counted the number of predictions that improved by at least 0.5. Methodological details appear in Appendix A8.

Sensitivity analyses

We planned the following sensitivity analyses, and pre-specified the endpoint for these analyses to be the between- group differences of the change over time of asthma control from baseline to 12 months.

Sensitivity analysis #1. Selection bias from loss to follow-up – covariate adjustment

In keeping with recommendations,^{48,49} we included in our longitudinal analysis model (described previously), in addition to the randomized treatment assignment and the pre-planned stratification variable (clinical site), the covariates that might be related to dropout and the primary outcome. Appendix A9.

Sensitivity Analysis #2. Nonignorable timing of data collection -- Global sensitivity analysis to irregular visit times and dropout

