study intervention. To that end, we modeled time using flexible splines. This approach is well-described in the statistical literature and implemented in standard statistical software packages. (4) With measures occurring over a continuous time line, and with final measures happening sometime before and some after the pre-planned 12-month goal, we compared the two randomized groups of patients as of the same, pre-planned 12-month time compared to baseline (date of randomization). We accomplished this task by estimating from our models the expected values or mean outcomes as of 0 months and 12 months. This task is routine with typical longitudinal data models, whether those models implement mixed effects or population averaged approaches. In either case, we estimated expected values at times 0 months and at 12 months. The contrast of interest in estimating the effects of the intervention versus control becomes a difference between groups of the within-group differences over time from 0 months to 12 months. This approach used all available data, distinguished, for example, between a final measurement at 11 months versus another at 14 months, and permitted standard methods of covariate adjustment for covariate imbalance arising out of the loss to follow up at any time during the study.

We consider our approach to be superior to some alternatives and especially to ad hoc approaches. First, we do not agree with conventional approaches that simply ignore discrepancies between pre-planned and actual interview times. If over time an intervention is effective in reducing asthma symptoms, then a patient should have a lower (better) asthma control score if he or she is interviewed at month 7 or 8 rather than at month 6. Second, we do not feel that treating time as categorical factor and adding a covariate that indicates whether the interview was inside or outside of a pre-specified window leads to unbiased estimates. There is little reason for this approach when time can be analyzed as a continuous measure. Third, approaches that use a patient's final measurement, even if it occurs before 12 months (pre-specified end date), as the final, 12-month measurement is simply another version of last observation carried forward (LOCF) approaches, which have been thoroughly discredited in numerous analyses, reports, and editorials. A final measurement at month 8 in theory will

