(2) "Exclusion restriction". The effect of the assignment to the home visitor arm of the study must influence outcome only through the actual completion of the home visit. A patient would have to react the same in terms of asthma outcome if he or she had been assigned to the home visitor treatment arm or the portal only arm, and had received no home visits. In the context of this study, this key assumption would be violated if the mere assignment to the home visitor led to higher expectations of improved asthma outcome just by learning of the assignment, and diminished expectations upon learning of assignment to the patient portal arm. Owing to the unavoidable fact that the patients could not be blinded to the treatment assignment, a violation of this assumption might be possible. But it might be that both the home-visitor patients and the portal-only patients could have similar expectations of some improvement merely by being recruited to the study and followed over time. A variation on this assumption requires that the patient who is randomized to the home visitor group but who does not schedule or see the home visitor (lack of compliance with the protocol) will receive no benefit from just being assigned to the home visit group. That assumption seems plausible in this setting.

(3) The final assumption, "monotonicity", requires that patients assigned to the portal group did not obtain home visits. Our design satisfied this assumption because only patients assigned to the home visit arm of the study were able to receive home visits. Although this assumption was very likely satisfied, meeting this assumption limits the inference of the effect of the home visitors to the patients with the characteristics of those who actually had the full set of home visits. To be able to generalize the effect of home visits to all patients would require yet an additional assumption – that the effect of treatment is the same across all patient types. We feel that this assumption could not be satisfied because home visits, almost by definition, are not going to produce the same reaction and outcome across a diverse group of patient who

Appendix A10 (continued). Estimating effect of home visitors adjusted for incomplete adherence – A sensitivity analysis.

have sometimes markedly different comorbidities, ages, educations, poverty levels, and home environment.

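### The primary contrast subtracts baseline ACQ in full; adjusting for it instead would cut the variance by roughly 10–35% (assumed correlation 0.4–0.7, irregular visits), with no new data

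*Combined protocol and SAP*

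**What the plan says.** Under *Modeling approach – flexible modeling of time* the SAP states: "The contrast (estimator) of interest was the difference between the treatment groups in the changes in expected values from 0 months to 12 months". Appendix A7 (*Methods for irregular data collection times*, item 4) repeats it as "a difference between groups of the within-group differences over time from 0 months to 12 months". *Study design* gives the reasoning: "The longitudinal design supports baseline measures as within-subject controls".

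The primary model is a marginal log-gamma GEE with a spline in time. *Model form* says: "By including splines for time and group-by-time interaction terms, these models could produce the expected values at 0 and 12 months". The equation is not printed. The group-by-time terms, the expected values at month 0, and the mention of treatment assignment as a model term under *Sensitivity analysis #1* together imply that the arms may differ freely at month 0.

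The only other adjustment named for the base model (*Model form*, Appendix A7) is clinic. The one full covariate list (Appendix A8) has a low/high severity class, which Table 3 builds from utilisation and treatment history, not from ACQ.

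On the order of events, Table 1 (week 0) reads: "Participant meets with a member of the research team for consent, enrollment, randomization, and baseline data collection". The envelope procedure was meant to "preserve allocation concealment until the patient gave consent and the envelope was unsealed", and Appendix A10 acknowledges that "the patients could not be blinded to the treatment assignment".

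**The concern.** Under randomisation the expected arm difference in baseline ACQ is zero, so whatever difference appears is noise. The most precise use of that noise is to remove the part that predicts the 12-month score, with a coefficient near the within-patient correlation. Full subtraction fixes the coefficient at 1 and adds variance whenever the correlation is below 1. The primary confidence interval is then wider than the collected data support.

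A second issue is conditional. If ACQ was asked after the envelope was opened, unblinded patients could report differently by arm at baseline. The planned contrast would carry the whole of that shift into the treatment effect. A baseline-adjusted estimate would carry only part of it.

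**Working it through.** **Inputs.** From the documents: 300 evaluable patients, 1:1 allocation, a difference of 1/3 SD, power 0.82–0.87 (*Statistical power*); visits at 0, 12, 24, 36 and 48 weeks (Appendix A7); linear spline with knots at 3, 6, 9 and 12 months (Appendix A8). Assumed, because the documents give no values: within-patient correlation ρ of 0.4–0.7, mean ACQ 2.0, coefficient of variation 0.55, the visit delays, and two-sided 5% testing.

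**1. The plan's own power.** Let D0 and D12 be the arm differences in mean ACQ in SD units, with n = 150 per arm.

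- Planned contrast: Var(D12 − D0) = 2(1 − ρ) × 2/150.
- Power = Φ((1/3)/SE − 1.96).
- At ρ = 0.5, SE = √(2/150) = 0.1155, and power = Φ(2.887 − 1.96) = 0.823.
- Solving for power 0.82 and 0.87 gives ρ = 0.496 and 0.563. The stated range is therefore consistent with full subtraction at ρ of about 0.50–0.56.

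**2. Closed form for adjustment** (two time points, complete data). Var(D12 − ρD0) = (1 − ρ²) × 2/150, so the variance ratio to the planned contrast is (1 + ρ)/2.

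| ρ | Ratio | Power, planned | Power, adjusted |
|---|---|---|---|
| 0.4 | 0.70 | 0.750 | 0.883 |
| 0.5 | 0.75 | 0.823 | 0.915 |
| 0.6 | 0.80 | 0.898 | 0.950 |
| 0.7 | 0.85 | 0.961 | 0.981 |

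At ρ = 0.496 and 0.563 the adjusted power is 0.914 and 0.937. The planned contrast would need 300/0.748 = 401 and 300/0.7815 = 384 patients to match.

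**3. Irregular visits, log-gamma GEE.** Simulated trials of 300 patients had an exponential delay (mean 1 month) at each post-baseline visit, gamma outcomes with exchangeable correlation, no true effect, and contrasts on the ACQ scale. Monte Carlo error of a ratio is about 0.02–0.03. Variance ratios with a constant mean:

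| Comparison | ρ 0.4 | 0.5 | 0.6 | 0.7 |
|---|---|---|---|---|
| Piecewise-linear baseline ACQ vs planned, both exchangeable | 0.81 | 0.86 | 0.91 | 0.91 |
| Same, both independence | 0.79 | 0.78 | 0.82 | 0.72 |
| Straight-line baseline ACQ vs planned, both exchangeable | 0.82 | 0.87 | 0.94 | 0.98 |
| Shared month-0 mean vs planned, both exchangeable | 0.81 | 0.83 | 0.87 | 0.90 |
| Same, both independence | 0.86 | 1.00 | 1.17 | 1.37 |
| Piecewise exchangeable vs planned independence | 0.75 | 0.74 | 0.74 | 0.66 |
| Planned contrast alone, exchangeable vs independence | 0.93 | 0.86 | 0.81 | 0.72 |

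The last row shows that part of the gain in the row above it comes from the working correlation alone. If mean ACQ falls from 2.0 to 1.6, the piecewise ratio, both exchangeable, is 0.68–0.76.

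**4. Other delay patterns.** Five patterns with 10% dropout gave these variance cuts:

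- Covariate adjustment, identity link, both independence: 19–37%.
- Covariate adjustment, log-gamma, both independence (three of the patterns): 28–35%.
- Shared month-0 mean, exchangeable or full GLS on both sides: 6–28%, lowest where few visits fell after month 12.

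An adjusted fit under independence set against a planned fit under exchangeable ranged from a 27% cut to an 18% increase (identity link). The working correlation must therefore be the same on both sides. A repeat of the recommended form with it matched gave ratios of 0.75–0.91 (constant mean) and 0.66 (falling mean, ρ = 0.4 only).

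**5. Baseline reporting shift.** Suppose baseline ACQ is reported 0.2 points higher in one arm. The planned contrast moves by 0.20. The adjusted one moves by about ρ × 0.2, which is 0.08 at ρ = 0.4 and 0.14 at ρ = 0.7. Simulated values were 0.20–0.21 for the planned contrast, and 0.076 and 0.137 for the adjusted one.

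**The case against.** The planned contrast is valid, and one model gives both the within-arm changes and their difference. The adjusted model cannot give within-arm change, so two models are needed, and patients with only a baseline interview leave its fit. This stands, which is why the within-arm changes and the planned contrast should stay in the report.

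The document is retrospective: 301 patients had been analysed, and Appendix A7 says its methods were fixed before outcomes were considered. If outcome fits had been seen, the adjusted estimate can only be supplementary and the primary interval does not narrow. That also stands.

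The gain depends on model form. A straight-line term gains almost nothing at ρ = 0.7, a shared mean under independence can lose precision, and the segments for baseline ACQ are a new choice. The 10–35% therefore applies only to the piecewise form with matched working correlation.

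Appendix A5 describes its model as the one used for asthma control and then names an independence working correlation, so independence is a fair inference for ACQ. It is still not stated there, and moving to exchangeable is a second change to declare.

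The order in Table 1 may be only a list; *Study Overview* places randomisation after portal training. That makes the order uncertain, so it should be confirmed rather than assumed.

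Finally, for a 0.5-point difference with SD 2.0 × 0.55 = 1.1, the two-point formula already gives the planned contrast power of about 0.95 at ρ = 0.4 and more above that. At that difference the benefit is mainly a narrower interval.

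**Conclusion.** The concern holds as a free improvement in precision, not as a validity error. The plan uses baseline ACQ only by full subtraction. Adjusting with a few linear segments and the same working correlation on both sides cuts the variance by roughly 10–35% for ρ of 0.4–0.7. The interval would be about 5–19% narrower (√0.90 = 0.949, √0.65 = 0.806), equivalent to about 334–462 patients under the planned contrast.

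These figures rest on an assumed ρ, mean, coefficient of variation and visit delays. The upper end arises under independence or with a falling mean; with a constant mean and exchangeable correlation the main simulation gave 9–19%. The stated power of 0.82–0.87 is not said to be wrong.

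The validity of the planned contrast itself depends on baseline ACQ having been taken before allocation was known, which the documents do not settle.

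**What to change.** 1. Estimate the 12-month arm difference in expected ACQ adjusted for baseline ACQ, in the same log-gamma GEE with the same 999-resample bootstrap. Regress post-baseline ACQ on baseline ACQ (a few linear segments, with knots stated), clinic, time spline, arm and arm-by-spline, and standardise over all patients.
2. State the working correlation for asthma control. Exchangeable was the more precise choice in the simulations.
3. Use a shared month-0 mean only as an alternative, with an exchangeable working correlation, and only if baseline ACQ preceded the opening of the envelope.
4. Confirm that order from visit records and state it. If it cannot be confirmed, do not use the shared mean, and report the 12-month arm difference without baseline ACQ as a sensitivity analysis.
5. Keep the within-arm changes, print the planned contrast beside the adjusted one, and give the date of the change. If outcome fits had been seen, label the adjusted estimate supplementary.
6. Tidy the wording: Appendices A7 and A8 differ on the primary model's covariates, the Appendix A8 model lists no arm terms, and Appendix A7 still describes a mixed model for the contrast that *Model form* assigns to the marginal model.

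The cost is SAP wording, a check of visit records and a re-run. Baseline ACQ is already collected at V1 (Appendix A1).
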